6.3 Safety and Tolerability Analysis

Safety and tolerability will be assessed with physical examinations, vital signs, clinical laboratory values, 12-lead ECG, use of concomitant medications, and AE reports. The frequencies of adverse events, serious adverse events and laboratory abnormalities between the participants across the treatment groups will be compared. The severity of cholinergic adverse events will be carefully evaluated taking the criteria in [Appendix 2](#) into consideration (modified from the latest version of the Common Terminology Criteria for Adverse Events (CTCAE)) as there is potential for an interaction between Posiphen and Donepezil through the inhibition of AChE, thereby resulting in increased cholinergic activity.

Subjects who dropout during the initial 3-week at-home treatment period will be discontinued and replaced by new subjects. If 4 subjects are discontinued due to adverse events a safety review will be conducted.

6.4 PK Analysis

Plasma concentration-time data will be analyzed by non-compartmental methods using SAS version 9.4 or greater. Calculations will be based on the actual sampling times recorded during the study. Since the study is blinded, all subjects' plasma will be included in the PK analysis. From the plasma concentration-time data, the following PK parameters will minimally be determined, as data permit: Area under the curve (AUC), Cmax, Tmax, t_{1/2}, and CL. Dose-proportionality may be assessed on Cmax and AUC as appropriate. Serial pre-dose trough concentrations Cmax will be assessed for the attainment of steady state.

Plasma concentration-time data for Posiphen will be listed and summarized descriptively (number of subjects (N), mean, median, standard deviation (SD), minimum (min), and maximum (max)) and graphically presented. PK parameters will be listed and summarized descriptively (N, mean, median, SD, min, max, and 95% CI) by each dose regimen. In addition, geometric means and between-subject coefficients of variation (CV) will be calculated.

6.5 Exploratory Pharmacodynamic and Efficacy Analysis

Pharmacodynamics and efficacy analyses will focus on exploratory endpoints outlining target engagement, pathway engagement and functional/cognitive measures being the reference stones of the exploratory analyses both for Part 1 and Part 2.

Analysis will include descriptive summary tables, listings and figures for Part 1 and Part 2 as well as combined analyses of dose/treatment groups from Part 1 and Part 2. Statistical comparisons will be descriptively performed for PD and efficacy parameters as well as the relationships between them using mixed models.

6.6 Criteria for the termination of the trial

The trial may be terminated by the Project Directors and/or the Sponsor based on issues of safety, feasibility, and Data Safety Monitoring Board (DSMB) recommendations.

6.7 Interim Analysis

No interim analysis is planned. However, after completion of Part 1 of the study, the plasma and CSF samples will be analyzed unblinded for the biomarkers to determine if changes are needed to the biomarkers to be measured in Part 2. Since the conduct of the study in Part 2 will be identical to the conduct of the study in Part 1, recruitment will continue uninterrupted. The only potential change between Part 1 and Part 2 are the biomarkers to be measured. Due to COVID-19 potentially causing recruitment challenges, at the time of intended analysis, Part 1 data may be analyzed should only 1 of the 2 cohorts in Part 1 be complete (e.g., 14 PD Patients, 5 AD

Patients). Only the full cohort would be unblinded, any patients not analyzed as part of the Part 1 analysis will be analyzed when that cohort is fully completed. Full details of all analyses will be detailed in the SAP.

7**STUDY DRUG AND CONCOMITANT MEDICATIONS****7.1 Name and Description of IP and Comparator**

Posiphen will be prepared in 5 mg, 10 mg, 20 mg, 40mg, and 80 mg HPMC hard capsule shells. Matching Placebo capsules (non-lactose compound) will be prepared with an inert inactive excipient generally recognized as safe for human pharmaceutical use.

7.2 Dosage

The study drug is to be taken orally; one capsule, once a day in the morning, with or without food, for 25 days \pm 2 days at home (depending on when the confinement visit is scheduled).

Participants must take 80% of all doses (across 25 \pm 2 days). Bottles will be examined in clinic at the pre-confinement visit to assess compliance overall and in the last week.

7.3 Packaging/Dispensing/Labeling

The study drug (Posiphen capsules and placebo capsules) will be manufactured under cGMP, in a manner to preserve the blind, i.e., identical color and shape opaque HPMC hard capsule shells and packaged 30 capsules per bottle.

The investigational drug supply will be shipped directly to the clinical sites to dispense to participants.

The dosing schedule and storage requirements will be clearly explained to the participants and caregiver before dispensing the study drug, and it will be printed on the labels.

All clinical trial material dispensed under this protocol will bear the requisite cautionary statement “CAUTION: Limited by Federal (United States) Law to Investigational Use Only”.

7.4 Storage

Both Posiphen capsules and the matching placebo capsules must be stored at room temperature (15-30 °C; 59-86 °F), protected from moisture, in a locked, temperature-controlled area with restricted staff access.

7.5 Drug Accountability

The investigator is responsible for investigational product reconciliation and records maintenance. In accordance with all applicable regulatory requirements, the investigator or designated site staff must maintain investigational product accountability records throughout the course of the study. The responsible person(s) will document the amount of investigational product dispensed to and returned by subjects. All used and unused study drug containers must be returned to the site for accountability. Once authorized by a clinical monitor, unused study

drug (including partially used bottles) may be destroyed on site per appropriate site SOPS or should be shipped back to the Sponsor for destruction.

7.6 Compliance

Site personnel will assess compliance based on the amount of study drug dispensed to and returned by the participants, together with any related information, including the administration of study drug by study staff during the confinement visit. Participants must take 80% of all doses at home (25 ± 2 days) depending on the confinement visit date. Site personnel will count capsules and evaluate compliance from the bottle at the pre-confinement visit.

Prior to the pre-confinement visit, site personnel will also contact the participant and study partner to remind them of the dose regimen, to ensure that the necessary level of compliance has been achieved to continue with the confinement visit procedures.

Site personnel will assess compliance at the pre-confinement visit and again at the time of admission for the confinement visit. If participants are found to be < 80% compliant the site must consult with the Project Directors and/or Medical Monitor regarding timing and conduct of the confinement visit procedures. It is possible that subjects will be discontinued early from the study due to insufficient drug compliance.

7.7 Breaking the Blind

Only in the case of an emergency, when knowledge of whether the participant has received the investigational product is essential for the clinical management or welfare of the participant, may the investigator request to unblind a participant's treatment assignment. If the investigator needs the blind to be unmasked for a subject for any reason, the investigator must contact the Medical Monitor and/or Project Directors to obtain an approval. If the blind is broken, whether it be by accident or for the welfare of the participant, the investigator MUST contact the Medical Monitor. Refer to the study procedures manual for detailed procedures related to breaking the blind and reporting.

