15.2 Reporting SAEs

Collection of serious adverse events will begin once informed consent is signed (regardless of study drug exposure) and will continue until 30 days following the last dose of study drug. All SAEs must be reported to the Medical Monitor, the Sponsor, Project Directors and the Coordinating Center within 24 hours of learning of the event. This in turn will trigger an alert to

the appropriate Coordinating Center personnel and Protocol Project Directors, which will lead to the initiation of the creation of the report. A notification will be sent to all participating sites and the DSMB once the report is available. Sites will inform their IRB of the event based on local IRB requirements. The Sponsor is the IND holder and is responsible for submitting any SAEs according to the FDA reporting requirements.

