16 DATA AND SAFETY MONITORING BOARD (DSMB)

A DSMB will review the safety information from the study on an ongoing basis. The DSMB, will identify the study-specific data parameters and format of the information to be reported, as well as the timing of reports based on the enrollment status of the study. The DSMB will initially be provided with data blinded to treatment status, but they may request unblinded data if there is a safety concern.

Additionally, the DSMB will be informed of the occurrence of any serious adverse events within 7 days of being reported to the Coordinating Center. The DSMB may at any time request additional information from the Coordinating Center.

Based on the review of safety data, the DSMB will make recommendations regarding the conduct of the study. These may include amending safety monitoring procedures, modifying the protocol or consent, terminating the study or continuing the study as designed. Using the Safety Review Process (review of lab data, vitals, and adverse events) and the DSMB, there is substantial oversight and case review to alert the investigators, in a timely manner, to any safety issues that may arise. Further details will be provided in the DSMB charter.

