18.2 Institutional Review Board (IRB)

Institutional Review Boards must be constituted, and their authority delegated through the institution's normal process of governance according to applicable State and Federal requirements for each participating location. Each participating institution must provide for the review and approval of this protocol and the associated informed consent documents and recruitment material by an appropriate IRB registered with the OHRP. Any amendments to the protocol or consent materials must also be approved before they are placed into use. In the United States, only institutions holding a current US Federal wide Assurance (FWA) issued by OHRP may participate. Refer to: <http://www.hhs.gov/ohrp/assurances/>.

The investigator must obtain approval from the IRB for all subsequent protocol amendments and, when warranted, changes to the informed consent document. Protocol and informed consent form amendments can be made only with the prior approval of the Coordinating Center. The investigator may not implement any protocol deviation without prior notification, review, and documented approval by the Study Director, except where necessary to eliminate an immediate hazard to study subjects, or when change(s) involve only logistical or administrative aspects of the trial. The investigator shall notify the IRB of deviations from the protocol or serious adverse events occurring at the site, in accordance with local procedures.

18.3 Informed Consent and Health Insurance and Portability and Accountability Act (HIPAA) Compliance

Informed consent will be obtained in accordance with 21CFR §50.25, and ICH Good Clinical Practice. Applicable HIPAA privacy notifications will be implemented, and HIPAA authorizations signed before protocol procedures are carried out. Information should be given in both oral and written form as deemed appropriate by the Site's IRB.

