3.3 Randomisation

For Part 1: For each cohort (AD, PD) up to 14 subjects will be randomised to posiphen or placebo in a ratio of 10 Active: 4 Placebo.

For Part 2: A sample size of up to 40 Early PD patients will be randomized to one of the 4 posiphen doses, 10 patients each dosed at 5 mg, 10 mg, 20 mg, or 40 mg.

The study is conducted in a blind manner and the randomization schedule for each cohort will be available once all patients in each cohort have completed the required schedule and the data have been locked for that cohort.

4. Population

Three analysis populations are defined for each of the three cohorts (Part 1 AD, Part 1 PD, Part 2 PD):

Intent to treat population

The Intention to treat population (ITT) includes all patients who received at least one dose of study medication and provide post baseline data. Analyses will be based on the treatment actually received and not necessarily that scheduled by the randomisation.

Safety population

The Safety population (Safety) includes all patients who received at least one dose of the study medication. Summaries of safety and tolerability will be based on the actual treatment received.

Pharmacokinetics population

The Pharmacokinetic population (PK) includes all patients who receive at least one dose of study medication and who provide sufficient data to enable parameter estimation.

5. Study Methods

Assessments will be made during three visits (Screening, Baseline and Confinement); in addition there are two telephone calls to assess for adverse events. Specific clinic procedures and details of all assessments performed are given in Section 9 of the protocol.

5.1 Schedule.

Details of all assessments performed with timings are given in Table 2.

Table 2: Clinical Assessments Schedule

Visit Timing	Day -42 to 0		Day 14 (± 4)	1-3 days prior to confinement	Days 25 (± 2)		
Procedures	Screening	Baseline	Phone	Pre- Confinement Phone Contact	Confinement		
					Admission	6-Hour Sampling	Discharge ^e
Informed Consent	X						
Demographics	X						
Medical and Psychiatric History	X						
Height and BMI	X						
Inclusion and Exclusion Criteria	X	X					
Urine Dipstick Pregnancy Test	X						
Physical and Neurological Examination	X	X			X		X
AD & PD: MMSE	X	X			X		
AD: CDR	X	X			X		
AD: ADAS-Cog 14		X			X		
AD & PD: WAIS-IV		X			X		
PD: MDS-UPDRS	X ^g	X			X		
C-SSRS	X	X			X		
Vital Signs ^b	X	X			X	X	X
Clinical Lab Safety Tests	X	X ⁱ			X ⁱ		
12-Lead ECG	X	X			X		X
MRI of Brain ^c	X						

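### Protocol 7.7 makes emergency unblinding of a participant conditional on prior approval, with no exception when no approver can be reached or delay would cause harm

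*Protocol*

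**What the plan says.** Protocol 7.7 has four elements that bear on this.

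- It limits unblinding to an emergency in which knowing whether the participant received the investigational product is essential to care or welfare. Only then "may the investigator request to unblind".
- It adds that if the blind must be "unmasked for a subject for any reason, the investigator must contact the Medical Monitor and/or Project Directors to obtain an approval".
- It requires contact with the Medical Monitor once the blind has been broken, whether by accident or for the participant's welfare.
- It closes with a pointer: "Refer to the study procedures manual for detailed procedures related to breaking the blind and reporting".

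Three other places touch on prior approval or on access to assignments.

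- Protocol 18.2 requires the Study Director's prior approval of protocol deviations, "except where necessary to eliminate an immediate hazard to study subjects" (it also exempts logistical or administrative changes).
- Protocol 16 says of the DSMB that "they may request unblinded data if there is a safety concern".
- SAP 3.3 says that "the randomization schedule for each cohort will be available once all patients in each cohort have completed the required schedule" and that cohort's data are locked.

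**The concern.** In an emergency where the assignment is needed, the investigator should be able to learn it without waiting for a study role to agree. As written, 7.7 puts an approval between the investigator and the code in the one situation where it accepts that the code is needed.

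The setting makes such a situation possible. Under Protocol 4.2 dosing is at home for 25±2 days, so an acute event can occur away from the clinic and outside working hours. Protocol 7.9.2 permits stable cholinesterase inhibitors, and 6.3 notes a possible interaction between Posiphen and donepezil. Protocol 7.8 describes cholinergic crisis with drugs of this class, and atypical blood pressure and heart rate responses when cholinomimetics are combined with quaternary anticholinergics. Whether a patient with cholinergic symptoms is on active drug or placebo could therefore bear on care. What is at stake is a delay in the care of one patient, not a study result.

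**Working it through.** The plan gives no figure on this point to reproduce. The check is a reading of the text, followed by a small calculation of how often the rule could apply.

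**Reading the text**

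1. *Does the approval rule cover emergencies?* Yes. The first sentence of 7.7 admits unblinding only in an emergency and gives the investigator a right to ask, not to act. The second sentence applies whatever the reason, so it includes that emergency.
2. *Who must approve?* The Medical Monitor and/or the Project Directors. One of them is enough. That lowers the chance that nobody answers but does not remove it.
3. *Does the third sentence waive approval?* Not in terms. It creates a duty to make contact after a break. It can be read as accepting a break made first for the patient's welfare, but it leaves the preceding sentence in force.
4. *Does 18.2 waive approval?* In part. It lifts the Study Director's prior approval of a deviation when there is an immediate hazard. Protocol 7.7 asks for approval from different roles and does not refer to 18.2. Permission to deviate also does not supply a means of reaching the code.
5. *Does other text give the treating investigator access?* Not in the protocol or SAP. Section 16 serves the DSMB, and SAP 3.3 concerns release of the schedule after cohort completion and lock. The procedures manual may give a route; it could not be checked.

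**How often it could matter**

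Inputs from Protocol 6.1: Part 1 has 14 AD and 14 PD patients, each group split 10 Posiphen to 4 placebo. Part 2 has 40 PD patients, all on Posiphen at 5, 10, 20 or 40 mg.

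The trigger in 7.7 is knowing whether the participant received the investigational product. In Part 2 that is known and only the dose is masked. Active versus placebo is uncertain for 14 + 14 = 28 patients.

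The documents give no rate of emergency unblinding. Assume a probability p between 0.1% and 1% per patient, independent across patients. Expected cases are n × p, and the chance of at least one is 1 − (1 − p)^n.

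| n | p | Expected cases | Chance of at least one |
|---|---|---|---|
| 28 | 0.1% | 28 × 0.001 = 0.028 | 1 − 0.999^28 = 2.8% |
| 28 | 1% | 28 × 0.01 = 0.28 | 1 − 0.99^28 = 24.5% |

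**The case against.** The strongest reply is that the protocol is a summary and the manual holds the detail. Emergency code access and out-of-hours contacts are what one would expect a manual on breaking the blind to contain, so the protocol's silence does not show that a route is missing. This stands as far as the route is concerned. A reader might infer that the trial has no means of emergency unblinding; the documents do not support that. But if the manual allows immediate unblinding, it conflicts with a rule in 7.7 that applies for any reason, and the two need to be aligned.

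A second reply is that 18.2 is a general exception that needs no cross-reference, and that the third sentence of 7.7 already expects a break for welfare followed by notification. Both are fair readings. They make 7.7 ambiguous rather than an absolute bar, but an emergency rule should not depend on combining two sections.

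A third reply is that little would change clinically. Overdose care in 7.8 follows signs and symptoms, with atropine titrated to effect. Protocol 4.2 expects no cholinomimetic effects at 80 mg, and 5.1 reports no SAEs in prior clinical studies. This stands and keeps the point small.

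Three stronger readings are tempting and should be set aside:

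- *Every kind of unblinding needs approval under 7.7.* It does not. Planned cohort unblinding and DSMB requests follow other routes; the rule concerns unblinding of one participant at the investigator's initiative.
- *SAP 3.3 locks the code away until a cohort is complete.* That section concerns release of the schedule once a cohort is complete and its data locked. It says nothing either way about emergency access.
- *All 68 patients are exposed equally.* Using 14 + 14 + 40 = 68 would give 0.068 to 0.68 expected cases and a chance of at least one of 6.6% to 49.5%. That overstates the matter, because assignment to active drug is not in doubt for the 40 Part 2 patients.

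**Conclusion.** The point holds for the protocol text. Section 7.7 requires approval before an investigator unblinds a participant, does so even in the emergency it describes, and makes no provision for an unreachable approver or a harmful delay. The softening clauses do not clearly remove the requirement.

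The size is small: 0.028 to 0.28 expected cases among the 28 Part 1 patients, resting on an assumed 0.1% to 1% need for emergency unblinding and on the site knowing which part a patient is in. No endpoint, sample size or analysis model is affected. This is a cheap improvement for patient safety, not a flaw in the trial's inference. What the procedures manual says remains open.

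**What to change.** Add to 7.7 that, in a medical emergency where the treatment assignment is essential to care, the investigator may break the code at once without prior approval, must notify the Medical Monitor promptly afterwards, and must record the date and reason. A limit for that notice could be borrowed from the SAE rule in 15.2, "within 24 hours of learning of the event"; the exact limit is a matter of preference. Keep prior approval for non-emergency requests. Name the means of access to the code, and align the procedures manual.

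The cost is a sentence or two, a check of the manual, and a means of emergency code access if none exists. The downside is an occasional extra code break, which would be logged. It removes no patient from analysis by rule. SAP section 4 says "The Intention to treat population (ITT) includes all patients who received at least one dose of study medication and provide post baseline data", and neither that definition nor those of the Safety and PK populations excludes an unblinded patient.

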7.8 Overdose

No specific antidote for the overdose of Posiphen is known; however, signs or symptoms of possible overdose should be noted and treated. The Medical Monitor and Project Directors should be notified as well. Because strategies for the management of overdose are continually evolving, it is advisable to contact a poison control center to determine the latest recommendations for the management of an overdose of any drug. Although Posiphen is a weak AChE inhibitor, based upon overdose information published in prescribing information for related products, overdose with AChE inhibitors can result in cholinergic crisis characterized by severe nausea, vomiting, salivation, sweating, bradycardia, hypotension, respiratory depression, collapse and convulsions. Increasing muscle weakness is a possibility and may result in death if respiratory muscles are involved. Tertiary anti-cholinergics such as atropine may be used as an antidote for overdosage. Intravenous atropine sulfate titrated to effect is recommended. Atypical responses in blood pressure (BP) and HR have been reported with other cholinomimetics when

co-administered with quaternary anticholinergics such as glycopyrrolate. It is not known whether dialysis (hemodialysis, peritoneal dialysis, or hemofiltration) is an effective treatment for overdose.

